5.1. Inclusion Criteria

Participants are eligible to be included in the study only if all of the following criteria apply:

Type of Study Participant and Disease Characteristics

- [1] Have a diagnosis of T1DM for at least 1 year. A diagnosis of T1DM is based on medical history with a fasting C-peptide ≤ 0.30 nmol/L at screening or before randomization.
- [2] Have been using MDIs without interruption for at least 3 months prior to screening.

Study Participant Characteristics

- [3a] No male contraception required except in compliance with specific local government study requirements.
- [3b] Female participants:
 - 1) Women of child-bearing potential who are abstinent (if this is complete abstinence, as their preferred and usual lifestyle) or in a same sex relationship (as part of their preferred and usual lifestyle) must agree to either remain abstinent or stay in a same sex relationship without sexual relationships with males. Periodic abstinence (e.g., calendar, ovulation, symptothermal, post-ovulation methods), declaration of abstinence just for the duration of a trial, and withdrawal are not acceptable methods of contraception.
 - 2) Otherwise, women of child-bearing potential participating must agree to use 1 highly effective method (less than 1% failure rate) of contraception, or a combination of 2 effective methods of contraception for the entirety of the study.
 - a) Women of child-bearing potential participating must test negative for pregnancy prior to initiation of treatment as indicated by a negative serum pregnancy test at the screening visit followed by a negative urine pregnancy test within 24 hours prior to exposure.

b) Either 1 highly effective method of contraception (such as combination oral contraceptives, implanted contraceptives or intrauterine device) or a combination of 2 effective methods of contraception (such as male or female condoms with spermicide, diaphragms with spermicide or cervical sponges) will be used. The participant may choose to use a double barrier method of contraception. Barrier protection methods without concomitant use of a spermicide are not a reliable or acceptable method. Thus, each barrier method must include use of a spermicide. It should be noted that the use of male and female condoms as a double barrier method is not considered acceptable due to the high failure rate when these methods are combined.

3) Women not of childbearing potential may participate and include those who are:

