- a) infertile due to surgical sterilization (hysterectomy, bilateral oophorectomy, or tubal ligation), congenital anomaly such as mullerian agenesis; or
- b) post-menopausal – defined as either
 - i) A woman at least 40 years of age with an intact uterus, not on hormone therapy, who has cessation of menses for at least 1 year without an alternative medical cause, AND a follicle-stimulating hormone (FSH) >40 mIU/mL; or
 - ii) A woman 55 or older not on hormone therapy, who has had at least 12 months of spontaneous amenorrhea; or
 - iii) A woman at least 55 years of age with a diagnosis of menopause prior to starting hormone replacement therapy.

[4] Are at least 18 years of age, at the time of signing the informed consent.

[5] Have HbA1c values of 5.6% to 9.5% inclusive, as determined by the central laboratory at screening.

[6] Have been treated with a stable regimen of once- or twice-daily insulin glargine (U-100 or U-300), insulin detemir, or insulin degludec (U-100 or U-200) for 3 months prior to screening.

[7] Are currently treated with the same SC rapid-acting analog insulin (insulin lispro U-100 or U-200, insulin aspart, FiAsp, or insulin glulisine) in MDI for at least the last 30 days prior to screening.

[8] Have a body mass index (BMI) $\leq 35 \text{ kg/m}^2$, with no significant weight gain or loss in the past 3 months ($\geq 5\%$).

[9] In the investigator's opinion, are well-motivated, capable, and willing to:

- learn how to self-inject treatment;
- maintain study diaries, as required for this protocol;

- wear study-provided CGM (Dexcom G6) during the complete study duration without interruption and use this device for therapeutic decision-making;
- must have a normal wake/sleep pattern such that midnight to 0600 hours will reliably reflect a usual sleeping period.

[10] In the investigator's opinion, are proficient in:

- counting carbohydrates
- adjusting meal- and correction boluses based on glucose readings with a stable insulin/carbohydrate ratio as well as correction factors
- adjusting insulin and dietary therapy during special situations (e.g., exercise, stress, intermittent diseases)

[11] Are willing and able to follow the visit schedule during the complete duration of the trial.

Informed Consent

[12] Capable of giving signed informed consent as described in Section [10.1](#), which includes compliance with the requirements and restrictions listed in the ICF and in this protocol.

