[24] Have any other serious disease or condition (e.g., known drug or alcohol abuse/regular consumption or psychiatric disorder) that, in the opinion of the investigator, would pose a significant risk to the patient, preclude the patient from following and completing the protocol, or interfere with the interpretation of safety, efficacy, or PD data.

Alcohol abuse/regular consumption is defined as an average daily intake of >3 units for males or >2 units for females within 6 months prior to the study.

One unit is equivalent to 8 g of alcohol: a half-pint (~240 mL) of beer, 1 glass (125 mL) of wine or 1 (25 mL) measure of spirits.

[25] Have had a blood transfusion or severe blood loss within 3 months prior to screening or have any hematologic condition that may interfere with HbA1c measurement (e.g., hemoglobinopathy, hemolytic anemia, sickle-cell disease).

[26] Have fasting triglycerides >400 mg/dL or non-fasting triglycerides >600 mg/dL.

[27] Women of childbearing potential who

- i) are pregnant or intend to become pregnant
- ii) are lactating/breastfeeding (including the use of a breast pump)
- iii) are unwilling to remain abstinent or use birth control as described in Appendix 4
- iv) test positive for pregnancy at the time of screening (Visit 1). Note: a urine pregnancy test is conducted at Visit 3.

Prior/Concomitant Therapy

[28] Are taking drugs that may significantly affect glycemic control (e.g., niacin [allowed if <1.0 g/day], bile acid sequestrants).

[29] Are receiving chronic (lasting longer than 14 consecutive days) systemic glucocorticoid therapy (including intravenous, intramuscular, SC, and oral) or intra-articular (but excluding topical, intraocular, intranasal, and inhaled preparations), or have received such therapy within 4 weeks immediately prior to screening with the exception of replacement therapy for adrenal insufficiency.

[30] Are currently taking or have taken within the 3 months preceding screening, prescription or over-the-counter medications to promote weight loss. Patients who participate must agree not to initiate a diet and/or exercise program during the study with the intent of reducing body weight other than the lifestyle and dietary measures for diabetes treatment.

[31] Are taking total daily dose of insulin >100 Units at the time of screening.

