10.4. Appendix 4: Contraceptive Guidance and Collection of Pregnancy Information

Definitions:

Woman of Childbearing Potential (WOCBP)

A woman is considered fertile following menarche and until becoming post-menopausal unless permanently sterile (see below).

If fertility is unclear (e.g., amenorrhea in adolescents or athletes) and a menstrual cycle cannot be confirmed before first dose of study intervention, additional evaluation should be considered.

Women in the following categories are not considered WOCBP

1. Premenarchal
2. Premenopausal female with 1 of the following:
 - Documented hysterectomy
 - Documented bilateral salpingectomy
 - Documented bilateral oophorectomy

For individuals with permanent infertility due to an alternate medical cause other than the above, (e.g., mullerian agenesis, androgen insensitivity), investigator discretion should be applied to determining study entry.

Note: Documentation can come from the site personnel's: review of the participant's medical records, medical examination, or medical history interview.

3. Postmenopausal female is defined as, women with:
 - i. A woman at least 40 years of age with an intact uterus, not on hormone therapy, who has cessation of menses for at least 1 year without an alternative medical cause, AND a follicle-stimulating hormone >40 mIU/mL; or
 - ii. A woman 55 or older not on hormone therapy, who has had at least 12 months of spontaneous amenorrhea; or
 - iii. A woman at least 55 years of age with a diagnosis of menopause prior to starting hormone replacement therapy.

The investigator will attempt to collect pregnancy information on any male participant's female partner who becomes pregnant while the male participant is in this study. This applies only to male participants who receive study intervention.

After obtaining the necessary signed informed consent from the pregnant female partner directly, the investigator will record pregnancy information on the appropriate form and submit it to the sponsor within 24 hours of learning of the partner's pregnancy. The female partner will also be followed to determine the outcome of the pregnancy. Information on the status of the mother and child will be forwarded to the sponsor. Generally, the follow-up will be no longer than 6 to 8 weeks following the estimated delivery date. Any termination of the pregnancy will be reported regardless of fetal status (presence or absence of anomalies) or indication for the procedure.

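### Section 5.1 and Appendix 4 disagree on whether a premenopausal woman with a tubal ligation is of childbearing potential, and the protocol's pregnancy tests and contraception rule depend on that status

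*Protocol*

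**What the plan says.** Section 5.1 of the protocol introduces its list with "Women not of childbearing potential may participate and include those who are". Item a) under that lead-in covers women who are "infertile due to surgical sterilization (hysterectomy, bilateral oophorectomy, or tubal ligation"), and also names congenital anomaly, with mullerian agenesis as the example. Item b) covers postmenopausal women.

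Appendix 4 (Section 10.4) defines the same status separately. Its default is "A woman is considered fertile following menarche and until becoming post-menopausal unless permanently sterile (see below"). Under "Women in the following categories are not considered WOCBP" it lists three procedures for premenopausal women: "Documented hysterectomy", "Documented bilateral salpingectomy" and bilateral oophorectomy, also documented. Tubal ligation is not mentioned. For permanent infertility from another medical cause, with mullerian agenesis and androgen insensitivity as examples, it leaves study entry to the investigator.

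Exclusion [27] in Section 5.2 is addressed to women of childbearing potential. Its third limb excludes those who "are unwilling to remain abstinent or use birth control as described in Appendix 4".

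**The concern.** Classification as a woman of childbearing potential decides whether the protocol requires a pregnancy test before the first dose, whether contraception is compulsory, and whether exclusion [27] applies at all. If two sections give different answers for the same woman, these safeguards depend on which section the site happens to read.

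The protocol treats exposure in pregnancy as something to prevent. Section 7.2 withdraws a participant who becomes pregnant, and Section 6.7.1 says washout of LY3209590 may take up to 10 weeks. Section 5 does not allow waivers of enrollment criteria, so a site cannot settle the conflict by asking for an exception.

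**Working it through.** No arithmetic applies. The check compares the two definitions category by category and then traces what depends on the result.

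**Step 1. The definitions side by side.**

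| Category | Section 5.1 [3b] 3) | Appendix 4 | Agreement |
|---|---|---|---|
| Hysterectomy | Not of childbearing potential | Not of childbearing potential | Yes |
| Bilateral oophorectomy | Not of childbearing potential | Not of childbearing potential | Yes |
| Tubal ligation, premenopausal | Named as not of childbearing potential | Not listed, so the fertile default applies | **No** |
| Bilateral salpingectomy | Not named, but the lead-in is open-ended | Named as not of childbearing potential | Unclear |
| Mullerian agenesis | Named as not of childbearing potential | Study entry at the investigator's discretion | Partial |
| Postmenopausal, three definitions | Same three | Same three | Yes |

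Only the tubal ligation row is a direct conflict. One text names the procedure as conferring infertility. The other applies a default of fertility and leaves the procedure off its list of exceptions.

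**Step 2. What depends on the status.**

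- Section 5.1 [3b] 2): contraception, a negative serum test at screening and a negative urine test within 24 hours before exposure.
- Schedule of Activities (Section 1.3): the serum test at Visit 1 and the urine test at Visit 3, both restricted to women of childbearing potential.
- Appendix 2, footnote b: the same two tests, plus a urine test at Visit 801 or ED2.
- Exclusion [27]: all four limbs, including current pregnancy and a positive test at Visit 1.

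**Step 3. One woman under each definition.** Take a premenopausal woman with a tubal ligation and no other relevant history.

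- Classified by Section 5.1, she falls outside every item in Step 2. She can be randomized and given her first dose at Visit 3 with no protocol-required pregnancy test.
- Classified by Appendix 4, with that status carried into the same rules, she needs the Visit 1 and Visit 3 tests and falls under the contraception requirement and exclusion [27].

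**Step 4. Is there a rule of precedence?** The serum-test row of the schedule carries a note pointing to Section 5.1. The urine-test row has no such pointer, and neither does Appendix 2 footnote b. No passage says that Section 5.1 prevails over Appendix 4, or the reverse.

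**The case against.** The best defence is that Section 5.1 is the working text. It contains the contraception rule, both pre-dose tests and its own list of women to whom they do not apply, and the serum-test row cites it. Exclusion [27] cites Appendix 4 only for birth control, not for who counts as being of childbearing potential. This stands in part: it makes Section 5.1 the more natural reading. It does not remove Appendix 4, which states a definition of the same term under the same protocol and reaches a different answer.

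A second defence is that Appendix 4's list is not closed, because it has a discretion clause and advises further evaluation where fertility is unclear. The discretion clause does not clearly reach tubal ligation. Its examples are congenital or genetic, and it concerns study entry rather than testing or contraception.

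Three stronger readings are tempting, and the documents do not support them.

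- A reader might infer that a woman with a bilateral salpingectomy gets the mirror-image result, fertile under Section 5.1. The lead-in there is non-exhaustive, and a site can reasonably treat salpingectomy as surgical sterilization.
- A reader might infer that pregnancy status would never be checked. Appendix 2 allows further tests at the investigator's discretion, and the schedule allows them where local regulations require. Section 4.1.1 also mentions the Visit 3 urine test in general terms, although it refers to the schedule, where the row is restricted. The accurate statement is that no test is clearly required by the protocol.
- A reader might infer that a site using Appendix 4 would screen-fail such a woman for not using contraception. That would follow only if she were unwilling to comply. The methods in Section 5.1 are also given as examples, so a site might consider the ligation itself to be her method. Whether it qualifies is a medical question, and the difference in testing would remain either way.

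**Conclusion.** The inconsistency is real and is firm for tubal ligation. For bilateral salpingectomy and mullerian agenesis it is a difference in wording that could produce different handling but need not. The consequence is a site-dependent gap in protocol-required pregnancy testing, and possibly in contraception, for premenopausal women with a tubal ligation.

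Its size cannot be derived from the documents. A headcount among the approximately 238 planned participants would need the share who are women, the share of those who are premenopausal, and the share of those with a tubal ligation, and none of these is given. The point does not depend on the count.

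It concerns eligibility and participant safety only. The primary endpoint, estimand, alpha level, sample size and analysis are unaffected. The conclusion assumes that Appendix 4's reference to permanent sterility is tied to the list that follows it, as its wording indicates. Which definition is clinically right is not decided here.

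**What to change.** Reconcile Section 5.1 [3b] 3)a and Appendix 4 into one definition of women not of childbearing potential. It should cover both the surgical and the congenital categories, because aligning the surgical list alone would leave the mullerian agenesis difference in place. Exclusion [27], both pregnancy-test rows of the Schedule of Activities and Appendix 2 footnote b should then refer to that definition. The sponsor's medical team decides which categories it contains.

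The cost is a wording change, a memo to sites and, depending on the definition chosen, possibly a few extra pregnancy tests of a kind already in the schedule.

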5.2. Exclusion Criteria

Participants are excluded from the study if any of the following criteria apply:

Medical Conditions

- [13] Have had more than 1 emergency room visit or hospitalization due to poor glucose control (hyperglycemia or diabetic ketoacidosis [DKA]) within 6 months prior to screening.
- [14] Have had any episodes of severe hypoglycemia (defined as requiring assistance due to neurologically disabling hypoglycemia) and/or hypoglycemia unawareness within the 6 months prior to screening.
- [15] Have significant lipohypertrophy, lipoatrophy, scars, or h/o abscess in areas of injection.
- [16] Have vision or hearing loss that impairs recognition of CGM screens, alerts and alarms.
- [17] Cardiovascular (CV): have had any of the follow CV conditions: acute myocardial infarction, New York Heart Association Class III or IV heart failure (Section [10.6](#)), or cerebrovascular accident (stroke)
- [18] Gastrointestinal: have gastroparesis or have undergone gastric bypass (bariatric) surgery or restrictive bariatric surgery (e.g., Lap-Band®) prior to screening

[19] Hepatic: have acute or chronic hepatitis, or obvious clinical signs or symptoms of any other liver disease except non-alcoholic fatty liver disease (NAFLD) (i.e., patients with NAFLD are eligible for participation), and/or have elevated liver enzyme measurements, as determined by the central laboratory at screening and as indicated below:

- Total bilirubin level (TBL) >2 x the upper limit of normal (ULN), or
- Alanine aminotransferase (ALT)/serum glutamic pyruvic transaminase (SGPT) >2.5 x ULN, or
- Aspartate aminotransferase (AST)/serum glutamic oxaloacetic transaminase (SGOT) >2.5 x ULN

[20] Renal:

- Have history of renal transplantation
- Are currently receiving renal dialysis
- Have serum creatinine >2.0 mg/dL (177 μ mol/L) at screening, or
- Have an estimated glomerular filtration rate (eGFR) of <30 mL/min/1.73 m^2

[21] Have experienced significant weight loss or gain ($>5\%$) in body weight in the 3 months prior to screening.

[22] Have active or untreated malignancy, or have been in remission from clinically significant malignancy (other than basal cell or squamous cell skin cancer) for less than 5 years or are at increased risk for developing cancer or a recurrence of cancer in the opinion of the investigator.

[23] Have known hypersensitivity or allergy to any of the study medications or their excipients.

[24] Have any other serious disease or condition (e.g., known drug or alcohol abuse/regular consumption or psychiatric disorder) that, in the opinion of the investigator, would pose a significant risk to the patient, preclude the patient from following and completing the protocol, or interfere with the interpretation of safety, efficacy, or PD data.

Alcohol abuse/regular consumption is defined as an average daily intake of >3 units for males or >2 units for females within 6 months prior to the study.

One unit is equivalent to 8 g of alcohol: a half-pint (~240 mL) of beer, 1 glass (125 mL) of wine or 1 (25 mL) measure of spirits.

[25] Have had a blood transfusion or severe blood loss within 3 months prior to screening or have any hematologic condition that may interfere with HbA1c measurement (e.g., hemoglobinopathy, hemolytic anemia, sickle-cell disease).

[26] Have fasting triglycerides >400 mg/dL or non-fasting triglycerides >600 mg/dL.

[27] Women of childbearing potential who

- i) are pregnant or intend to become pregnant
- ii) are lactating/breastfeeding (including the use of a breast pump)
- iii) are unwilling to remain abstinent or use birth control as described in Appendix 4
- iv) test positive for pregnancy at the time of screening (Visit 1). Note: a urine pregnancy test is conducted at Visit 3.

Prior/Concomitant Therapy

[28] Are taking drugs that may significantly affect glycemic control (e.g., niacin [allowed if <1.0 g/day], bile acid sequestrants).

[29] Are receiving chronic (lasting longer than 14 consecutive days) systemic glucocorticoid therapy (including intravenous, intramuscular, SC, and oral) or intra-articular (but excluding topical, intraocular, intranasal, and inhaled preparations), or have received such therapy within 4 weeks immediately prior to screening with the exception of replacement therapy for adrenal insufficiency.

[30] Are currently taking or have taken within the 3 months preceding screening, prescription or over-the-counter medications to promote weight loss. Patients who participate must agree not to initiate a diet and/or exercise program during the study with the intent of reducing body weight other than the lifestyle and dietary measures for diabetes treatment.

[31] Are taking total daily dose of insulin >100 Units at the time of screening.

[32] Are receiving any oral or injectable medication intended for the treatment of diabetes mellitus other than rapid-acting and basal analog insulin in MDI in the 90 days prior to screening.

[33] Are using or have used blood pressure-lowering medication at a dose that has not been stable for 1 month prior to screening.

Prior/Concurrent Clinical Trial Experience

[34] Are currently enrolled in any other clinical study involving an IP or any other type of medical research judged not to be scientifically or medically compatible with this study.

[35] Have participated, within the last 30 days in a clinical trial involving an IP. If the previous IP has a long half-life, 3 months or 5 half-lives (whichever is longer) should have passed.

[36] Have previously completed or withdrawn from this study or any other study investigating LY3209590.

Other Exclusions

- [37] Are investigator site personnel directly affiliated with this study and/or their immediate families. Immediate family is defined as a spouse, parent, child, or sibling, whether biological or legally adopted.
- [38] Are Lilly employees.

5.3. Lifestyle Considerations

Per the Schedule of Activities (Section 1.3), qualified medical staff will provide diabetes management counseling, which will include instructions on diet and exercise and education about the signs, symptoms, and treatment of hypoglycemia, should it occur.

Prescription or over the counter (OTC) medications that promote weight loss are exclusionary if used within 3 months prior to screening (study entry), or between screening and randomization. These medications are also not allowed at any time during the treatment period. If started after randomization, these medications should be immediately withdrawn.

Study participants should be instructed not to donate blood or blood products during the study or for 4 weeks following the study.

